## 2.9 Risk/Benefit Assessment

### 2.9.1 Potential Risks

Blood drawing may cause discomfort, bruising, light-headedness or fainting. Rarely, a blood draw may result in infection at the site of venipuncture. Nasal swab collection may cause irritation or dryness at the sampling sites for a short time, usually less than 5 minutes.

Some subjects in the trial will get Placebo instead of the MVA-BN-RSV vaccine. The Placebo consists of the MVA-BN formulation buffer TBS. Placebos are harmless, inactive substances made to look like the real vaccine, used in the clinical trial and contain no active ingredient. The subject may experience discomfort at the injection site, such as pain.

Preclinical data with recombinant MVA-BN-RSV vaccine in rats and rabbits have revealed no special hazard for humans based on conventional studies of safety.

There is substantial safety data available for the vector backbone MVA-BN and for other MVA-based recombinant vaccines in healthy and immunocompromised subjects as well as the first safety data for the MVA-BN-RSV vaccine (Phase I clinical trial RSV-MVA-001 in healthy adult subjects; see [Section 2.6](#)). Adverse reactions in this trial setting are expected to be comparable to adverse reactions previously reported for MVA-BN or MVA-BN based recombinant vaccines and/or those typically seen with other modern vaccines. Main risks involve the development of local reactions at the injection site, e.g. erythema, pain, swelling and induration.

As with all vaccines, there is a risk of an allergic reaction or an anaphylactic event. Trial site staff will watch subjects for at least 30 minutes after each vaccination and in the event that a severe allergic reaction and/or dyspnea might occur, appropriate medical treatment and supervision will be readily available.

## 2.9.2 Benefits

There will be no direct benefit to the trial participants. Trial participants will contribute significantly to the development of a RSV vaccine which is a potential benefit for adults with underlying cardiovascular or pulmonary disease, elderly and children to reduce their risk of severe illness and mortality due to infection with RSV. In addition based on the current immunogenicity and efficacy data collected in non-clinical and clinical studies with MVA-BN, participants in clinical trials are expected to acquire protection against smallpox infection and might potentially also acquire protection against disease symptoms caused by RSV. The immunogenicity results of the first clinical trial with the MVA-BN-RSV vaccine indicate that RSV specific humoral and cellular immune responses are significantly boosted by the vaccine. However, it cannot be said if the vaccine is efficacious against the disease, as data available up to date are limited and do not allow for conclusions on protection against RSV.

Analysis of the samples collected will not directly benefit the subject.

## 3 Objectives

Refer to trial protocol synopsis [Section 1.5](#).

## 4 Trial Design

### 4.1 Experimental Design Forecast

A randomized, single-blind, placebo controlled, dose-ranging Phase II trial in  $\geq 55$  year old adults to evaluate the safety and immunogenicity of the recombinant MVA-BN-RSV vaccine.

In total 400 subjects will be recruited into the main trial. Subjects will receive two administrations 4 weeks apart which will consist of MVA-BN-RSV Dose 1, MVA-BN-RSV Dose 2 or placebo (TBS). To obtain Dose 1 the vaccine will be diluted in TBS according to the vaccination instructions. For details on the treatment groups see [Table 13](#).

Approximately one year after their first vaccination 86 subjects in the selected treatment groups of the main trial will be recruited to participate in the booster substudy and will receive one dose of MVA-BN-RSV vaccine.

Recruitment into the main trial will be performed into a staggered manner as outlined below. Any occurring events as defined in the trial halting rules in [Section 4.5](#) would stop the staggering procedure until further clarification.

#### Staggering Procedure:

The staggering process will be performed at one clinical trial site. The main trial will start with a sentinel cohort with 2 subjects, of whom one subject will be recruited into Group 2 and the other subject into Group 4 (i.e. 1:1 subjects receiving Dose 1 and Dose 2). Each subject will receive a priming vaccination followed 4 weeks later by a boosting vaccination of the same dose. Safety will be assessed prior to and 3 days post first vaccination. Safety assessments will be based on solicited and unsolicited adverse event data evaluated by the Safety Monitoring Team (SMT) comprising of the national coordinating investigator, investigator and the medical monitors (BN and CRO). Following a positive safety assessment after the first vaccination in both subjects recruited into the sentinel cohort, recruitment in the safety cohort will start.

The safety cohort will include a total of 10 subjects: 5 subjects will be recruited each into Groups 2 and 4 (i.e. 5:5 subjects receiving Dose 1 and Dose 2). Following a positive safety assessment by the SMT based upon solicited and unsolicited adverse event data 3 days post first vaccination recruitment in all groups for the remaining subjects will be opened.

The principal investigator, national coordinating investigator and the medical monitors (BN and CRO) must participate in the SMT meeting and decide on the next staggering step. Project leader BN, Contract Research Organization (CRO), statistician and Clinical Research Associate (CRA) can participate in the meeting, if further information on the trial conduct is required, but will not participate in the decision to go to the next staggering step. In total, two staggering steps and SMT meetings are required until all groups can be recruited in parallel.

**Table 13 Treatment Groups Main Trial**

Group	N	Age [years]	Volume per dose [mL]	1 st vaccination Day 0 [Inf.U]	2 nd vaccination Day 28 [Inf.U]	Route
1	80	≥ 55	0.5	1 x 10 	Placebo	IM
2	80	≥ 55	0.5	1 x 10 	1 x 10 	IM
3	80	≥ 55	0.5	5 x 10 	Placebo	IM
4	80	≥ 55	0.5	5 x 10 	5 x 10 	IM
5	80	≥ 55	0.5	Placebo	Placebo	IM
Total	400					

### Booster Substudy

In total 86 evaluable subjects will receive a booster vaccination approximately one year after their first vaccination in the main trial receiving the same dose they received during the main trial. To obtain 40 evaluable subjects per group up to 43 subjects per selected group will be recruited. Subjects are then followed up for 12 months after their last vaccination.

## 4.2 Description of Trial Procedures

The trial procedures will be conducted according to the trial procedure schedule ([Section 1.5](#), [Section 1.6](#) and [Section 1.7](#)) and as described on the following pages. Visits must be scheduled within the intervals/visit windows given below.

### 4.2.1 Main Trial

#### 4.2.1.1 Screening Phase

All subjects must be thoroughly informed of all aspects of the trial (e.g. trial visit schedule, required evaluations and procedures, risks and benefits) as described in the informed consent form (ICF). The ICF and the statement about the HIPAA must be reviewed with the subject and signed and dated by the subject and the investigator, or person designated by the investigator, who conducted the informed consent discussion before proceeding with any evaluations or procedures required by this protocol.

After ICF has been collected, subjects will enter a screening period of up to 28 days before the first vaccination.

Screening Visit (Days -28 to -1)

The following tasks will be performed:
 

• Subject to read, sign and date ICF and HIPAA

• Check inclusion/exclusion criteria

• Obtain medical history

Screening Visit (Days -28 to -1)

• Complete physical examination including auscultation of heart and lungs and measurement of body weight and height

• Evaluation of vital signs

• Perform Electrocardiogram (ECG) reading

• Recording of prior and concomitant medication

• Counseling on avoidance of pregnancy: Review of acceptable contraceptive methods and recent menstrual history with WOCBP

• Recording of AEs/SAEs

• Blood draw for safety laboratory 22 mL including

○ Serum pregnancy test (WOCBP only)

○ Hematology & serum chemistry

○ Hepatitis B and C; HIV

○ Troponin I

○ If applicable: HbA1c (additional blood draw of 3 mL)

If a subject is screened and cannot be vaccinated because of a certain transient condition (e.g. abnormal lab value due to an acute condition or a missing lab evaluation e.g. due to mishandling of the sample), then the subject can be re-screened on one further occasion only and the respective test(s) should be repeated as a “partial” re-screening rather than a full re-screening. The re-Screening Visit must be within the 28 day window started by the first Screening Visit and the window Day -28 to -1 before first vaccination must not be exceeded. If a subject cannot be vaccinated due to other circumstances (e.g. completion of a wash-out period for a medication or vaccine not allowed during the trial) or the 28 day period is exceeded, the complete Screening Visit needs to be repeated and a new Screening number will be assigned. The clock then re-starts at the re-screening visit with Day -28 before the first vaccination.

#### 4.2.1.2 Active Trial Phase

After successfully passing the screening evaluations, the eligible volunteers can enter the active trial phase (Visit 1 to EAP) starting with Visit 1 and ending at either EAP or premature discontinuation.

The first 12 subjects are recruited in a staggered fashion. After completion of the staggering steps all remaining subjects can be vaccinated. The staggering process is described in detail in [Section 4.1](#) and in the Synopsis in [Section 1.5](#).

The procedures performed at Visit 1 and all following visits are listed below. **Collection of immunogenicity samples and all other examinations listed above the vaccination event must always be performed prior to vaccine/TBS administration.**

At Visit 1/Day 0, subjects will receive the first vaccination with 0.5 mL of the recombinant MVA-BN-RSV or TBS given IM preferably in the non-dominant upper arm. Subjects will be blinded to the treatment assignment, i.e. will not be told which group they were assigned until after completion of the main trial.

Following each vaccination subjects will be kept under close observation at the clinical trial site for at least 30 minutes, with appropriate medical treatment readily available in case of a rare anaphylactic reaction following the vaccine administration. Any AEs that occur during or after vaccine administration will be recorded.

Solicited local and general AEs will be collected on a memory aid, completed by the subject for an 8-day period (Days 0-7), beginning with the day of vaccination. The memory aid will be returned to the clinic staff at the following visit. If symptoms persist at Day 7, daily symptoms and temperature will continue to be measured each day until resolved and the last day of symptoms and maximum intensity is recorded on the memory aid.

### Visit 1 (Day 0)

#### Tasks to be performed prior to randomization and vaccination:

- Confirmation of inclusion / exclusion criteria
- Targeted physical examination including auscultation of the heart and lungs
- Evaluation of vital signs
- Recording of concomitant medication
- Counseling on avoidance of pregnancy: Review of acceptable contraceptive methods and recent menstrual history with WOCBP
- Recording of AEs/SAEs
- Urine pregnancy test (WOCBP only)
- Blood draw for serum collection (9 mL)
- Nasal swab collection for mucosal immune response (swabs are taken from both nostrils)
- **Only for the subgroup: PBMC collection (64 mL)**

**If eligible for participation in this trial the subject will be randomized (for the first 12 subjects please refer to [Sections 1.5](#) and [4.1](#). for details on the staggering procedure). The following tasks will be performed after randomization:**

- First MVA-BN-RSV vaccination
- Subject observation by CTS staff for at least 30 minutes after vaccination
- Recording of immediate AEs/SAEs
- Handout of memory aid for first vaccination, ruler and thermometer

### Visit 1 (Day 0)

**Temporary deferral of vaccination:** If an acute illness is present the subject may be vaccinated at a later date within the accepted time window. The vaccine/TBS can be administered to persons with a minor illness such as diarrhea or any other mild condition with or without low-grade febrile illness, i.e. oral temperature  $< 100.4^{\circ}\text{F}$  ( $< 38.0^{\circ}\text{C}$ ). In case of minor illness involving the upper respiratory tract, such as mild upper respiratory infection, with or without low-grade febrile illness, the vaccination should be deferred within the accepted time window, until the subject is symptom-free.

### Visit VS (V1 + 3-4 days)

Sentinel Cohort, Safety Cohort (first 12 [2 + 10] subjects)

**Groups 2 and 4**

**The following tasks will be performed:**

- Recording of concomitant medication
- Recording of AEs/SAEs
- Review of the memory aid handed out at Visit 1  
*Note: transfer entries to eCRF for SMT review within 24 hours, keep photocopy of the memory aid and return original to the subject to complete entries for the remaining days.*
- Examination of the injection site

**Only if clinically indicated:**

- Nasal swab collection for Respiratory Viral Panel (RVP) PCR in case of symptoms indicating a respiratory infection

### Visit 1b (V1 + 7-9 days)

**Subgroup only**

**The following tasks will be performed:**

- Targeted physical exam incl. auscultation of the heart and lung
- Evaluation of vital signs
- Recording of concomitant medication
- Recording of AEs/SAEs
- Review of the Memory Aid Card handed out at Visit 1
- Collection of the Memory Aid Card
- Blood draw for serum collection (9 mL) and PBMC collection (64 mL)
- Nasal swab collection for mucosal immune response (swabs are taken from both nostrils)

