Recording of immediate AEs/ SAEs after vaccination 		■				■					
Handout of memory aid 		■				■					
Review/ of memory aid 			■	◆	■		◆	■			
Collection of memory aid 				◆	■		◆	■			
Examination of injection site		■	◆	■			◆	■			

■ = mandatory; □ = in case of medical need or any underlying condition that requires further examinations; ◆ = Subgroup only

 Review of acceptable contraceptive methods and recent menstrual history with WOCBP.

 New SAEs, new AEs indicating a respiratory tract infection and changes to AEs/SAEs ongoing at the previous visit only.

 At Screening Visit, a serum pregnancy test must be performed. At all other visits, a urine pregnancy test is to be performed.

 Additional safety measures can be taken at any other trial visit or at unscheduled visits, if clinically indicated.

 Approximate amounts of single blood draws: Safety lab: 11 mL (at V2, V4, FU1 and FU2; if applicable), including hematology (3 mL), serum chemistry (including pregnancy test; 8 mL), virology: 5ml (at SCR:)Hepatitis B and C, HIV); Safety lab 17 mL (at SCR), including all above plus HbA1c (3 mL; if

applicable); Troponin I: 3 mL; serum collection (antibody testing): 9 mL; PBMC collection (T cell collection): 64 mL. Maximal total amount of blood taken/subject: up to 176 mL (642 mL for subjects in the  subgroup).

 The memory aid should be completed daily for an 8-day period (Day 0 to Day 7), starting with the day of vaccination. If symptoms are ongoing after Day 7, temperature/symptom measurements should continue each day until resolved and the last day of the symptom and maximum intensity will be recorded on the memory aid.

 The entries on the memory aid card need to be reviewed together with the subject.

 Only in the presence of symptoms indicating a respiratory infection at any time point after first vaccination, defined by any case of rhinorrhea, nasal congestion, pharyngitis, cough, wheezing (or increase in baseline wheezing), sputum production (or increase / change in nature of baseline sputum production) or new (or worsening of) shortness of breath. Subjects need to be instructed to return to the site within 3 days after start of symptoms.

 Subgroup only.

 Refer to [Section 8.2.9](#) for Cardiac Assessment

 Nasal swabs will be taken from both nostrils.

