**Visit 2 (V1 + 12-16 days)**

**The following tasks will be performed:**

- Targeted physical examination including auscultation of the heart and lungs
- Evaluation of vital signs
- Recording of concomitant medication
- Recording of AEs/SAEs
- Blood draw for safety laboratory (hematology & serum chemistry, 11 mL)
- Blood draw for serum collection (9 mL)
- Nasal swab collection for mucosal immune response (swabs are taken from both nostrils)
- Review of the memory aid handed out at Visit 1
- Collection of the memory aid
- Examination of the injection site
- **Only for the subgroup: PBMC collection (64 mL)**

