**Booster Visit 1b (BV1 + 7-9 days)**  
**Subgroup only**

- Recording of AEs/SAEs
- Review of the memory aid handed out at BV1
- Collection of the memory aid
- Blood draw for serum collection (9 mL) and PBMC collection (64 mL)
- Nasal swab collection for mucosal immune response (swabs are taken from both nostrils)
- Examination of the injection site

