#### Duration of an AE will be calculated as follows:

For Unsolicited AEs: expressed in [days]

- End date – start date of AE + 1 day. Note that duration can be calculated even if time of day is missing for either start or end dates, or if time is missing for both.
- In case of partially missing start date (month and/or day missing) or partially missing end date (month and/or day missing), duration will not be calculated.
- In case of an ongoing AE, the duration will not be calculated.

For Solicited AEs: expressed in [days]

- End date of AE – start date of AE + 1, where end date is the last day the symptom is defined as an AE and start date is the first day symptom is defined as an AE (no matter if the AE occurred at every day between first day and last day). In case of an ongoing AE, the duration will not be calculated.

Relative day of onset between vaccination and start of AE will be calculated as follows:

For Unsolicited AEs: expressed in [days]

- Start date of AE – corresponding vaccination date.
- In case of (partially) missing start date no calculation will be done.

For Solicited AEs: expressed in [days]

- The relative day is calculated as the day of first symptom intensity recording > 0.
- Start date of AE – corresponding vaccination date, where start date is the first day a symptom is defined as an AE; vaccination day corresponds to Day 0.

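### In the PBMC subgroup the memory aid is collected at +7-9 days with no return rule, although it must be filled in through Day 7 and until symptoms resolve, and the same card is listed for collection again at +12-16 days

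*Protocol*

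**What the plan says.** **Diary period.** Footnote 6 to the Main Trial Schedule (Protocol 1.6) states: "The memory aid should be completed daily for an 8-day period (Day 0 to Day 7), starting with the day of vaccination". For symptoms that outlast the diary week, the same footnote adds: "temperature/symptom measurements should continue each day until resolved and the last day of the symptom and maximum intensity will be recorded on the memory aid". Protocol 1.7 (footnote 6), the opening text of 4.2.1.2 and 4.2.2.2, and Section 8.2.6 repeat both rules.

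**First collection, subgroup only.** At V1b (V1 + 7-9 days) the tasks include review of the card and then "Collection of the Memory Aid Card". V3b (V3 + 7-9 days) and BV1b (BV1 + 7-9 days) likewise list "Collection of the memory aid". None of the three says the card goes back to the subject. The opening text of 4.2.1.2 and 4.2.2.2 has the card handed in at the next visit, which for this subgroup is V1b or BV1b.

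**Second collection, everyone.** V2 (V1 + 12-16 days) lists "Review of the memory aid handed out at Visit 1" and collection of that same card. V4 and BV2 do the same. The schedules mark these steps as mandatory, with no exemption for the subgroup.

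**The exception.** At the staggering visit VS, 3-4 days after the first vaccination, the site must "keep photocopy of the memory aid and return original to the subject to complete entries for the remaining days".

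**Analysis.** The duration of solicited local and general AEs is part of the secondary safety endpoints (Protocol 1.5). For solicited AEs, main SAP 3.3.4 states: "In case of an ongoing AE, the duration will not be calculated". Booster SAP 4.3.4 has the same rule. Under main SAP 3.3.2 and booster SAP 4.3.2, an AE with neither an end date nor an ongoing flag is treated as ongoing, and no end date is imputed.

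**The concern.** A site cannot both take the card on Day 7, 8 or 9 and leave it with the subject for entries until resolution. VS has a rule that resolves this; V1b, V3b and BV1b do not. Some sites may hand the card back, because V2, V4 and BV2 expect it again, while others keep it. Capture of reactions lasting beyond about a week would then depend on site habit.

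Two things are at stake. A subject seen on Day 7 may hand in the card before that day's entry is complete. A subject with ongoing symptoms on any of Days 7-9 may have no card on which to write the last day and the peak intensity. If the end date is never recovered, the SAP rule leaves that reaction out of the duration summary. The reactions most exposed to this are the long ones. The booster SAP (4.5.8) also divides solicited local AE incidence by subjects whose memory aid was completed, without saying whether a card taken on Day 7 counts as completed.

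**Working it through.** **Plan's own figure.** Day 0 to Day 7 inclusive is 7 - 0 + 1 = 8 daily entries, which matches the stated 8-day period.

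**What has been observed at each visit day d.** Fully elapsed diary days = min(8, d). With duration defined in the SAPs as end - start + 1, the longest duration that the card can close for a Day 0 onset is d + 1.

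| Visit | Day d | Diary days fully elapsed | Longest closable duration (days) |
|---|---|---|---|
| V1b, V3b, BV1b | 7 | 7 of 8 | 8 |
| V1b, V3b, BV1b | 8 | 8 of 8 | 9 |
| V1b, V3b, BV1b | 9 | 8 of 8 | 10 |
| V2, V4, BV2 | 12 | 8 of 8 | 13 |
| V2, V4, BV2 | 16 | 8 of 8 | 17 |

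Only Day 7, one of three permitted days, cuts the diary short, and then only for part of one day. Later entries are at risk on all three days if the card is kept.

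**Who is exposed.**
- Main trial: 20 subjects in each of 5 groups = 100; 100/400 = 25%, at two visits each (V1b, V3b).
- Booster: about 26/86 = 30%, at one visit (BV1b).
- Day 7 visits: the documents give no distribution of visit days. If attendance is uniform over Days 7-9 (assumed), 100/3 = about 33 main-trial subjects per vaccination (range 0-100) and 26/3 = about 9 booster subjects (range 0-26).

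**Effect on mean duration, main trial.** The documents give no durations for this trial, so these are assumptions: a share p = 5% or 10% of reactions outlasts the card and truly lasts 14 days, the rest average 4 days, every late end date is lost in the subgroup, and none is lost in the other 75%.

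- True mean = (1 - p) x 4 + p x 14, which is 4.5 days at p = 0.05 and 5.0 days at p = 0.10.
- Reported mean = [0.75 x true mean + 0.25 x (1 - p) x 4] / [0.75 + 0.25 x (1 - p)].
- p = 0.05: (3.375 + 0.95) / 0.9875 = 4.38 against 4.5, or 2.7% low.
- p = 0.10: (3.75 + 0.90) / 0.975 = 4.77 against 5.0, or 4.6% low.

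These are upper figures for the stated p, because they assume that no late end date in the subgroup is recovered.

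**The case against.** The strongest reply is that capture does not stop when the card is first taken. V2, V4 and BV2 list review and collection of the same card. Section 8.2.6 has the investigator gather solicited data over the following visits, and AE recording continues at later visits. End dates can therefore still reach the eCRF. At a Day 7 visit the entries are reviewed with the subject, oral temperature is taken and the injection site is examined, so part of Day 7 is seen.

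This stands, and it limits the point. A reader might infer that the last diary day is lost throughout the subgroup, that subjects have nowhere to record later symptoms, and that the SAPs then remove the longest reactions. The documents do not support this. Day 8 and Day 9 visits lose no diary day, the second collection implies that the card may still be in use, and the SAPs omit only AEs still recorded as ongoing, not every reaction unresolved at V1b. What the reply does not supply is a return instruction. Without one, the exact last day and the peak intensity after collection rest on recall.

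A second reply is that long reactions may be rare. Protocol 2.6 reports that all solicited AEs in the Phase I trial resolved within 8 days, with a median of at most 5. That is reassuring but limited: 54 vaccinees aged 18-65, at no more than 1 x 10^8 TCID50, whereas this trial enrols from age 55 and adds 5 x 10^8 Inf.U. Treating the result as 0 of 54 subjects, the two-sided 95% upper limit is 1 - 0.025^(1/54) = 6.6%. A 5% share is compatible with that; 10% is a high scenario.

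Third, the SAP rule applies to all arms and the subgroup is planned at 20 per arm, so any loss should be balanced. That also stands.

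**Conclusion.** The protocol contradicts itself for the PBMC subgroup: the card is to be kept until symptoms resolve, collected at +7-9 days without a return rule, and collected again at +12-16 days. The consequence is less complete data on a secondary endpoint in up to 25% of planned main-trial subjects and about 30% of booster subjects. It does not threaten the comparison between arms. The last diary day is shortened at about one third of subgroup visits under uniform attendance (assumed; 0-100% possible). The late course of ongoing reactions is exposed on all three permitted days.

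The effect on mean duration in the pooled main trial is about 3-5% low, given the assumed 4-day and 14-day durations, a 5-10% share of long reactions and complete loss of late end dates in the subgroup. A reader might take the bias to be 11-20% by comparing 4.0 with 4.5 and 5.0 days. That drops ongoing reactions in every subject, whereas early collection concerns a quarter of them. The point is minor, and worth making because the repair is nearly free.

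**What to change.** **Protocol.** Reconcile the schedules and footnotes in 1.6 and 1.7, the opening text of 4.2.1.2 and 4.2.2.2, and the task lists for V1b, V2, V3b, V4, BV1b and BV2. At V1b, V3b and BV1b, replace collection with the rule already used at VS: review the card, photocopy it and return the original. Keep V2, V4 and BV2 as the single final collection for everyone; by Day 12-16 all 8 diary days have elapsed. Carry the change into the schedule copies in main SAP Section 2 and booster SAP Appendix 6.2.

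**SAPs.** Beside each solicited AE duration summary (main tables 14.3.1.2.7-8 and 14.3.1.3.7-8; booster tables 15.3.1.2.3 and 15.3.1.3.3), print the number of solicited AEs still recorded as ongoing and therefore left out. The duration rule itself need not change.

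**Cost.** Three task-list lines, matching edits to the two schedules and opening texts, and one count per duration table. No visit, sample or dose changes. The downside is an occasional lost card, for which the photocopy preserves the entries made up to that visit.
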